4.4.4 Derived Other Variables

4.4.4.1 Age for Demographics

Calendar age (in months) calculated using date of birth collected at time of visit 01 will be used in the analysis.

Following age groups will be derived, corresponding to stratification factor:

- < 12 months: until the last day before the 1st birthday date
- ≥ 12 months: from 1st birthday date

4.4.4.2 Participant duration

The duration of a participant participation in the study is computed in days as follows: maximum (date of visit, date of termination form) - date of visit 01 +1.

4.4.4.3 Duration of the Study

The duration of the study is computed in days as follows: maximum of all participants (date of visit, date of termination form) - minimum for all participants (date of visit 01) +1.

5 Statistical Methods and Determination of Sample Size

The statistical analyses will be performed under the responsibility of the Sponsor's Biostatistics platform using SAS® Version 9.4 software or later.

The results of the statistical analysis will be available in the clinical study report (CSR).

For descriptive purposes, the following statistics will be presented:

Table 5.1: Descriptive statistics produced

Baseline characteristics and follow-up description	Categorical data	Number of participants. Percentage of participants.
	Continuous data	Mean, standard deviation, quartiles, minimum, and maximum.
Clinical safety results	Categorical data	Solicited: Number and percentage (95% CIs) of participants. Unsolicited: Number and percentage (95% CIs) of participants, and number of events.
Immunogenicity / Shedding results	Categorical data (cutoff)	Number and percentage (95% CIs) of participants.
	Continuous data (titer / data)	Log10: Mean and standard deviation. Anti-Log10 (work on Log10 distribution, and anti-Log10 applied): Geometric mean, 95% CI of the geometric mean, quartiles, minimum, and maximum. Graphical representation by Reverse Cumulative Distribution Curve (RCDC) for immunogenicity.
Infectivity results	Categorical data	Number and percentage (95% CIs) of participants.
Efficacy results	Categorical data	Number and percentage (95% CIs) of participants, number of events, Vaccine Efficacy (VE) and 95% CI.

The statistical methodology will be based on the use of two-sided 95% confidence intervals (CI).

The Confidence Interval (CI) for the single proportion will be calculated using the exact binomial method (Clopper-Pearson method, quoted by Newcombe (1), i.e., using the inverse of the beta integral with SAS®).

For immunogenicity results, assuming that Log10 transformation of the titers/titers ratio follows a normal distribution, at first, the mean and the 95% CI will be calculated on Log10 (titers/titers ratio) using the usual calculation for normal distribution (using Student's t distribution with n-1 degree of freedom), then antilog transformations will be applied to the results of calculations, in order to provide geometric mean titers (GMTs) and geometric mean titers ratios (GMTRs) and their 95% CI.

$$GM \text{ is defined as follows: } GM = \left(\prod_{i=1}^n Y_i \right)^{1/n} = 10^{\left(\frac{1}{n} \sum_{i=1}^n \log_{10}(Y_i) \right)},$$

where (y_1, y_2, \dots, y_n) are the observed titers or individual ratios for each participant.

CIs for VE will be calculated using the Exact method described by Breslow & Day (2).

5.1 Statistical Methods

Statistical analyses will be conducted by cohort and cohorts pooled, as applicable on specific periods of time (e.g., D0-D56 after vaccination 1 for Cohorts 1, 2, 3 and 4; D56-D84 after vaccination 2 for Cohorts 2 and 4).

When applicable, analyses will be presented by baseline serostatus and overall.

5.1.1 Hypotheses and Statistical Methods for Primary Objectives

5.1.1.1 Hypotheses

All analyses will be descriptive; no hypothesis will be tested.

5.1.1.2 Statistical Methods

The data for any participant infected by laboratory confirmed wt RSV will be excluded from immunogenicity and viral shedding analyses from the date of wt RSV infection.

A short complementary analysis will be done without the exclusion of data to compare results.

Safety

Solicited adverse reactions (ARs), unsolicited AEs (including SAEs), MAAEs and AESIs will be summarized as described in Table 5.1. The main parameters will be described with 95% CI. At least the following parameters will be presented by vaccine group after each and any vaccination, in all participants regardless of baseline serostatus:

- Unsolicited systemic AEs occurring within 30 minutes of administration (immediate unsolicited AEs)

- Solicited administration site reactions and solicited systemic reactions within 28 days after each and any administration according to presence, time period, time of onset, intensity, number of days of presence, action taken, and whether the reaction led to early termination from the study. When more than 1 intensity level is reported within a time period, the highest intensity will be used.
- Unsolicited AEs occurring within 28 days after each and any administration by system organ class (SOC) and preferred term (PT), relationship, intensity, time of onset, duration and whether the AE led to early termination from the study.
- All SAEs that occur throughout the study by SOC and PT, seriousness criteria, time of onset, outcome, relationship, and whether the SAE led to early termination throughout the study
- All MAAEs and AESIs reported within 28 days after each and any vaccination by SOC and PT and relationship

Bayesian approach

A Bayesian approach based on Posterior Distribution may be applied to assess the difference between each RSV formulation and placebo group on the following safety endpoints (and/or other endpoint of interest):

- Any Grade ≥ 3 LRI
- Grade 3 fever

The probability that the difference of percentages of events between one RSV formulation and Placebo is greater than a pre-specified margin (δ) can be calculated based on posterior distribution, using non-informative prior Beta (1,1) (3) and observed binomial data:

Proba (%RSV - %Placebo > δ)

With:

- %RSV = (number of events / number of participants) in RSV group
- %Placebo = (number of events / number of participants) in Placebo group

If this probability is high (e.g., $\geq 80\%$) then it may be recommended to drop the formulation.

To assess the Bayesian probability that the percentage of events in RSV group is greater than a predefined value (δ) in comparison to Placebo, the posterior distribution of the difference (RSV - Placebo) would be computed using:

- a non-informative prior distribution: incidence of events in each group (p_i) follows uniform distribution (0,1)
- the likelihood of the observed data: Binomial distribution (n_i, p_i), n_i = number of assessed participants in each group, p_i = incidence of the events in each group
- The posterior distribution is the density distribution of the parameter P_i combining 1) the prior distribution and 2) the observed data.

- Posterior distribution: Beta (x_i+1, n_i-x_i+1), where x_i = number of events in each group and n_i = number of assessed participants in each group
- From the density distribution of P_{RSV} and $P_{Placebo}$, determine the density of the groups difference: simulate 1 000 000 pairs of observations and determine the proportion of difference ($P_{RSV} - P_{Placebo}$) $> \delta$.

Immunogenicity

The point estimates and their 95% CI of the following parameters will be presented for RSV A neutralizing antibody titers by D56 for Cohorts 1, 2, 3 and 4, and by D84 for Cohorts 2 and 4, for each vaccine group in RSV-naive participants:

- GMT
- GMTR based on the baseline neutralizing Ab titer
- Seroresponse rates defined as percentage of participants with a ≥ 4 -fold rise in RSV A serum neutralizing antibody titers based on the baseline value.
- Reverse cumulative distribution curves (RCDCs) will be presented
- Pairwise comparisons between vaccine groups may be conducted as exploratory analyses to compare seroresponse rates or GMTs for descriptive purpose.

The 95% CIs of the difference of proportions between 2 groups would be computed using the Wilson Score method without continuity correction. CIs of ratio of GMTs between 2 groups will be computed from the difference in means of log10 transformed titers between 2 groups with normal approximation.

Seroresponse using various thresholds regarding fold-rise or post-vaccination titer value may also be presented, as applicable. 4-fold rise seroresponse rate may be also presented by country/racial origin.

A Bayesian approach may be also applied to assess the seroresponse rate of RSV formulation by calculating the Bayesian probability that the percentage of participants with a ≥ 4 -fold rise in RSV A serum neutralizing antibody titers is greater than a predefined value.

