Placebo recipients will be included in each cohort to establish the background rates of respiratory and febrile illnesses that occur in infants and toddlers.

Clinical hypothesis:

Both doses of the live-attenuated RSV Δ NS2/ Δ 1313/I1314L vaccine are anticipated to be safe and immunogenic in infants and toddlers. However, administration of either dose may be associated

with adverse events that become apparent only when analyzed in a larger number of participants than the numbers enrolled in Laboratory of Infectious Disease (LID)/ National Institute of Allergy and Infectious Diseases (NIAID)/NIH Phase Ia studies, where each study assessed 10 to 40 vaccinees. Additionally, the rate, magnitude and durability of antibody responses may differ according to dose, as well as the magnitude of the memory (anamnestic) seroresponse observed following naturally occurring RSV infection. The intranasal [REDACTED] device used in this study may also impact the safety and immunogenicity of the vaccine. Dose selection will be based on a descriptive comparison of the safety, infectivity and immunogenicity of 1 or 2 administrations of either dose category.

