9.1.1.3.6 Assessment of Causality

The Investigator will assess the ***causal relationship*** between each unsolicited systemic AE and the product administered as either ***not related*** or ***related***, based on the following definitions:

- Not related – The AE is clearly / most probably caused by other etiologies such as an underlying condition, therapeutic intervention, or concomitant therapy; or the delay between vaccination and the onset of the AE is incompatible with a causal relationship; or the AE started before the first vaccination
- Related – There is a “reasonable possibility” that the AE was caused by the product administered, meaning that there is evidence or arguments to suggest a causal relationship

Note: By convention, all AEs reported at the administration site (whether solicited or unsolicited) and all solicited systemic AEs are considered to be related to the administered product and therefore are referred to as reactions and do not require the Investigator’s opinion on relatedness.

Adverse events likely to be related to the product, whether serious or not, that persist at the end of the study will be followed up by the Investigator until their complete disappearance or the stabilization of the participant’s condition. The Investigator will inform the Sponsor of the date of final disappearance of the event or the date of “chronicity” establishment.

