5.5 Determination of Sample Size and Power Calculation

No sample size calculation was done as there are no statistical hypotheses in this study.

A total of 300 participants are planned to be enrolled into 1 of the 4 cohorts sequentially:

- Cohort 1 (1 administration): 40 participants, i.e., 20 per vaccine group (RSV low-dose or placebo)
- Cohort 2 (2 administrations): 40 participants, i.e., 20 per vaccine group (RSV low-dose or placebo)
- Cohort 3 (1 administration): 40 participants, i.e., 20 per vaccine group (RSV high-dose or placebo)

- Cohort 4 (2 administrations): 180 participants, i.e., 60 per vaccine group (RSV high-dose or RSV low-dose or placebo).

Although there are no statistically powered hypotheses and no sample size computation in this study, the sample size of 100 participants in the RSV low-dose group (20 from Cohort 1, 20 from Cohort 2 and 60 from Cohort 4) will provide a probability of 95% to observe an event that has a true incidence of 3%. The sample size of 80 participants in the RSV high-dose group (20 from Cohort 3 and 60 from Cohort 4) will provide a probability of 95% to observe an event that has a true incidence of 3.75%.

A total of 300 participants are planned to be enrolled in the study. This corresponds to 120 participants in Placebo group, 100 participants in RSV low-dose group and 80 participants in RSV high-dose group. Table 5.2 below presents the number of participants by serostatus, in total and by RSV group, according to varying possible RSV-experienced rates ranging from 5% to 35% (derived from LID/NIH screening data) and provides a global overview of the proportion of RSV-naive/RSV-experienced participants that will be enrolled in the study.

Table 5.2: Number of Participants by Serostatus, in Total and by RSV Group, According to Varying Possible RSV-experienced Rates Ranging from 5% to 35%

% RSV-experienced	Total (N=300)		RSV low-dose group (N=100)		RSV high-dose group (N=80)	
	#RSV-experienced	#RSV-naive	#RSV-experienced	#RSV-naive	#RSV-experienced	#RSV-naive
5%	15	285	5	95	4	76
10%	30	270	10	90	8	72
15%	45	255	15	85	12	68
20%	60	240	20	80	16	64
25%	75	225	25	75	20	60
30%	90	210	30	70	24	56
35%	105	195	35	65	28	52

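### For the primary safety endpoints the plan commits only to per-arm percentages with single-arm intervals; the one RSV-versus-placebo safety comparison is optional, names two severe events and promises no interval

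*SAP*

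**What the plan says.** **Committed output.** SAP 5.1.1.2 (Safety) introduces its list of primary safety parameters with "At least the following parameters will be presented by vaccine group after each and any vaccination, in all participants regardless of baseline serostatus". It points to SAP Table 5.1, where clinical safety results are numbers and percentages of participants with 95% intervals, plus event counts for unsolicited events. SAP Section 5 gives the method: "The Confidence Interval (CI) for the single proportion will be calculated using the exact binomial method". Protocol 12.1.1.2 commits to the same. Neither document commits to a risk difference, a ratio or any between-group interval for safety.

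**Optional comparison.** The same SAP section says a Bayesian approach "may be applied to assess the difference between each RSV formulation and placebo group on the following safety endpoints". The endpoints are Grade 3 or higher lower respiratory illness (LRI) and Grade 3 fever, and the SAP allows others of interest. The output is the posterior probability that the RSV-minus-placebo difference exceeds a margin. The SAP gives that margin no value; protocol Section 15 uses 5% as an example.

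**Between-group interval.** A Wilson-score interval without continuity correction for a difference of proportions is named in both documents, but only under Immunogenicity.

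**Role of placebo and causality.** Protocol 5.1.2 states: "Placebo recipients will be included in each cohort to establish the background rates of respiratory and febrile illnesses that occur in infants and toddlers". Under protocol 9.1.1.3.6, administration-site events and "all solicited systemic AEs are considered to be related to the administered product", whichever product that was.

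**Framework.** SAP 5.1.1.1: "All analyses will be descriptive; no hypothesis will be tested".

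**The concern.** Runny nose, congestion, fever and irritability occur in children aged 6 to 18 months without any vaccine. Because solicited reactions are classed as related in every arm, the relatedness column cannot separate vaccine effect from background. Only the contrast with the randomised placebo children can do that. The plan commits to the ingredients of that contrast but not to the contrast or its uncertainty.

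Two things are at stake. A reader of the safety tables has two separate intervals per endpoint and may compare them by eye, which is much less sensitive than an interval for the difference. In addition, protocol 5.1.2 bases dose selection on a descriptive comparison of safety, infectivity and immunogenicity between the doses, and no between-dose safety estimate is committed either. By contrast, SAP 5.1.3 does commit to vaccine efficacy against placebo with an exact interval, which is an exploratory objective.

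**Working it through.** **1. The plan's own safety figure.** SAP 5.5 gives the chance of seeing at least one event in one RSV group.
- Low dose: 1 − (1 − 0.03)^100 = 95.2%.
- High dose: 1 − (1 − 0.0375)^80 = 95.3%.

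Both agree with the stated 95%. They are single-arm figures, the SAP words them that way, and they say nothing about a contrast with placebo.

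**2. Inputs for the contrast.** Cohort 4 has 60 per arm (SAP 5.5). Single-arm intervals are Clopper-Pearson 95% (SAP Section 5). The difference interval is Wilson-score 95% without continuity correction (SAP 5.1.1.2, Immunogenicity). The documents give no expected event rates, so the rates below are assumptions over a range.

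**3. One worked table.** Take 36/60 (60%) on RSV and 24/60 (40%) on placebo.
- Clopper-Pearson: 46.5% to 72.4% and 27.6% to 53.5%. These overlap.
- Single-arm Wilson limits: 47.37% to 71.43% and 28.57% to 52.63%.
- Lower limit of the difference: d − √[(p1 − l1)² + (u2 − p2)²] = 0.20 − √(0.1263² + 0.1263²) = 0.021.
- Upper limit: d + √[(u1 − p1)² + (p2 − l2)²] = 0.20 + √(0.1143² + 0.1143²) = 0.362.

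The difference is 20.0 points (2.1 to 36.2). The overlapping single-arm intervals conceal a difference whose interval excludes zero.

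**4. How often this happens.** For each pair of true rates I enumerated every pair of binomial outcomes at 60 versus 60 and summed the probability of each condition.

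| True rates | Difference interval excludes 0 | Single-arm intervals do not overlap |
|---|---|---|
| 60% vs 40% | 61% | 21% |
| 40% vs 20% | 68% | 29% |
| 25% vs 10% | 58% | 20% |
| 15% vs 5% | 43% | 10% |
| 40% vs 40% | 5.1% | 0.3% |

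**5. Precision that would be reported.** At 18/60 versus 12/60 (30% vs 20%) the difference is 10.0 points (−5.5 to 24.9). At 6/60 versus 3/60 it is 5.0 points (−5.2 to 15.7). Showing this width is useful in itself: it tells the reader that an absence of visible excess is compatible with a sizeable one.

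**6. Whether the optional Bayesian output fills the gap.** If it were extended to the 18/60 versus 12/60 table, the posterior probability of a difference above 5 points is 0.73, and above zero 0.89. The answer depends on a margin the SAP leaves open, and no interval is promised.

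**The case against.** The strongest reply has four parts.

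- **A comparison with placebo does exist.** A reader might infer that the randomised placebo arm is never formally compared on safety. The documents do not support that. SAP 5.1.1.2 sets out prior, likelihood, posterior and 1,000,000 simulated pairs, with an example 80% threshold, and allows further endpoints. Protocol 5.1.6, 12.1.1.2 and Section 15 repeat the approach. The SAP also derives the density of the group difference, from which an interval could be taken. This stands. What remains is that the comparison is optional, names two severe events and promises no interval.
- **Overlap is not the plan's criterion.** A reader might infer that safety or dose will be judged by overlap of intervals. No section says so, and the trial is declared descriptive. This also stands: the table above illustrates a reader's loss and is not an operating characteristic of the plan.
- **Nothing is lost or biased.** Counts per arm are committed, so anyone can calculate the unadjusted difference, and the parameter list is a minimum. That is true, but a primary objective should not leave its key contrast to the reader. A descriptive interval tests no hypothesis, and the SAP already uses between-group intervals descriptively for immunogenicity.
- **Too many intervals.** Covering all cohorts, two grade cuts and every vaccination would mean 20 endpoints × 10 contrasts = 200 intervals. Those from the 20-versus-20 cohorts would inform little: for 40% versus 20%, the difference interval excludes zero only 29% of the time. This stands and limits the fix to a short list in Cohort 4.

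**Conclusion.** The concern holds as a gap in committed reporting. No primary safety endpoint has a committed difference from placebo with an interval, although the convention on relatedness and the stated purpose of placebo make that difference the only route to excess reactogenicity. It is not an invalid analysis, a biased estimate or an absence of any placebo comparison.

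For a reader comparing intervals in Cohort 4, the chance of seeing a true excess of 10 to 20 points falls from 43–68% to 10–29% across the assumed rates. That size rests on assumed event rates, on 60 children per arm contributing data, and on a reader who judges by overlap.

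SAP 5.5 needs no change: "will provide a probability of 95% to observe an event that has a true incidence of 3" per cent is already stated as a property of the low-dose group alone.

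**What to change.** In SAP 5.1.1.2 (Safety) and protocol 12.1.1.2, commit to the following descriptive output for Cohort 4 after each vaccination:

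- **Contrasts:** low dose minus placebo, high dose minus placebo, and high minus low dose.
- **Method:** difference in proportions with a two-sided 95% Wilson-score interval without continuity correction, as already named under Immunogenicity.
- **Endpoints:** each solicited reaction (any grade), any adverse event of special interest, any LRI, any medically attended adverse event and any unsolicited adverse event.

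Any pooled difference should be stratified by cohort and use only concurrently randomised placebo children. For low dose these come from Cohorts 1, 2 and 4 (20 + 20 + 60 = 100), and for high dose from Cohorts 3 and 4 (20 + 60 = 80). The full 120 are not a concurrent control for either dose.

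**Cost.** A few extra columns in existing tables and no new data. The list is 8 solicited reactions + 4 other endpoints = 12, times 3 contrasts and 2 vaccinations = 72 unadjusted intervals. If there were no true differences and each excluded zero 5% of the time, about 72 × 0.05 = 3.6 would do so by chance. A footnote should say that the intervals are descriptive and unadjusted for multiplicity.

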1.4 Rationale for the Study

Prior to RSV Δ NS2/ Δ 1313/I1314L vaccine, 3 RSV vaccine viruses with the NS2 gene deletion (rA2cp Δ NS2, rA2cp248/404 Δ NS2, and rA2cp530/1009 Δ NS2) had been evaluated in clinical studies (7). The rA2cp Δ NS2 candidate was over-attenuated for adults but under-attenuated for use in young children, whereas both rA2cp248/404 Δ NS2 and rA2cp530/1009 Δ NS2 were over-attenuated and insufficiently immunogenic in seronegative children. Based on these results RSV Δ NS2/ Δ 1313/I1314L was developed. In a recent Phase Ia study sponsored by the National Institutes of Health (NIH) in RSV seronegative children aged 6 to 24 months, (n=20) (23), at the [REDACTED] dose, RSV Δ NS2/ Δ 1313/I1314L was safe, had good infectivity (100% of vaccinated participants infected) and immunogenicity (80% of participants with a \geq 4-fold rise in neutralizing antibody titers) and primed for a strong anamnestic response to wt RSV infection in the post-RSV season surveillance.

The NIH proceeded to age de-escalate in order to evaluate RSV Δ NS2/ Δ 1313/I1314L in younger infants, aged 4 to 6 months, who are the likely primary target population for a live-attenuated RSV vaccine since they are at highest risk for severe RSV-associated LRI. This study is currently ongoing, with 2:1 randomization to receive either [REDACTED] of RSV Δ NS2/ Δ 1313 /I1314L or placebo, and a sample size of up to 30 infants (ClinicalTrials.gov Identifier: NCT01893554) (23). To date, data is available on 15 infants aged 4 to 6 months who have been enrolled up to date and have completed the post-vaccination Acute and Post-Acute Phase of follow-up. Based on this data, the vaccine was well tolerated at the [REDACTED] dose, infectivity was 100% and vaccine virus replication was limited. Immunogenicity data from this study is pending.

RSV Δ NS2/ Δ 1313/I1314L vaccine appears to be safe and immunogenic in RSV seronegative infants and toddlers aged 6 to 24 months; and appears to be safe with restricted shedding in infants aged 4 to 6 months. Based on NIH Phase I trial data, RSV Δ NS2/ Δ 1313/I1314L will be evaluated by Sanofi Pasteur for further clinical development.

2 Study Objectives

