6.5 Randomization and Allocation Procedures

An IRT will be implemented to assign the participant numbers and allocate vaccine groups with dose numbers to the participants at Visit 01.

At Visit 01 visit, participants who meet the inclusion/exclusion criteria and whose parent / guardian/ legally authorized representative signs the ICF will be randomly assigned to one of the vaccine groups, according to the cohort:

- Cohorts 1 and 2: RSV ΔNS2/Δ1313/I1314L [REDACTED] (RSV low-dose) or Placebo in a 1:1 ratio
- Cohort 3: RSV ΔNS2/Δ1313/I1314L [REDACTED] (RSV high-dose) or Placebo in a 1:1 ratio
- Cohort 4: RSV ΔNS2/Δ1313/I1314L [REDACTED] (RSV high-dose) or RSV ΔNS2/Δ1313/I1314L [REDACTED] (RSV low-dose) or Placebo in a 1:1:1 ratio

At Visit 01, randomization will be stratified by cohort and by age sub-group (< 12 months / ≥ 12 months).

Site staff will connect to the IRT, enter the identification and security information, and confirm a minimal amount of data in response to IRT prompts. The IRT will then provide the dose number assignment and have the site staff confirm it. The full detailed procedures are described in the Operating Guidelines. If the participant is not eligible to participate in the study, then the information will only be recorded on the participant recruitment log.

Participant numbers that are assigned by the IRT will consist of a 12-digit string (a 3-digit country identifier, a 4-digit study center identifier, and a 5-digit participant identifier). For example, Participant 840000100005 is the fifth participant enrolled in Center Number 1 in the US (840 being the US country code).

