5.1.2.2 Statistical Methods

Safety

The point estimates and their 95% CI of the following parameter will be presented 7 days after each vaccination (D7 for Cohorts 1, 2, 3 and 4, and D63 for Cohorts 2 and 4) for each vaccine group by baseline serostatus:

- Proportion of participants with detectable/quantified virus shedding
- Arithmetic mean of vaccine virus shedding measured by [REDACTED]

Infectivity

The point estimate and its 95% CI of the following parameters will be presented after vaccination 1 (D56) for Cohorts 1, 2, 3 and 4, and after vaccination 2 (D84) for Cohorts 2 and 4 for each vaccine group by baseline serostatus:

- Proportion of vaccinees infected with the vaccine virus. Infection defined as detection of vaccine virus strain in nasal swab by [REDACTED] and / or a \geq 4-fold rise in RSV A serum neutralizing antibody titers or RSV serum anti-F IgG antibody titers.

Immunogenicity

The point estimates of GMT and GMTR and their 95% CI will be presented by vaccine group for the following endpoints:

- RSV A serum neutralizing antibody titers by D56 for Cohorts 1, 2, 3 and 4, and by D84 for Cohorts 2 and 4, in RSV-experienced participants
- RSV serum anti-F IgG antibody titers by D56 for Cohorts 1, 2, 3 and 4, and by D84 for Cohorts 2 and 4 by baseline serostatus.
- RSV A serum neutralizing and anti-RSV F IgG antibody titers after RSV season or at least 5 months after last vaccine administration by baseline serostatus.

Seroresponse using various thresholds regarding fold-rise or post-vaccination titer value may also be presented, as applicable.

Main immunogenicity analyses will be presented by baseline serostatus and age group (< 12 months *versus* \geq 12 months).

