5.1.3 Statistical Methods for Exploratory Objectives

Safety

Solicited ARs, unsolicited AEs (including SAEs), MAAEs and AESIs will be summarized. Analyses described in Section 5.1.1.2 will be presented by vaccine group after each and any vaccination by baseline serostatus.

Immunogenicity

Similar analyses as described as for secondary immunogenicity objectives will be performed on exploratory immunogenicity endpoints.

Analyses on RSV A and RSV B serum anti-Gcc IgG antibody responses planned in the protocol will finally not be produced for this study, please refer to section 5.7 for the rationale.

Efficacy

RSV Medically attended respiratory illness collected during the RSV season will be summarized. The main parameters will be described with 95% CI. At least the following parameters will be presented by vaccine group:

- RSV medically attended acute respiratory illness (RSV MAARI) by SOC and PT, intensity, time of onset, and duration
- RSV medically attended lower respiratory tract illness (RSV MAALRI) by SOC and PT, intensity, time of onset, and duration
- Vaccine Efficacy (VE)

The VE of RSVt vaccine (low dose or high dose, as applicable) will be estimated for each endpoint as follows:

$$VE = 1 - \frac{C_{RSV}/N_{RSV}}{C_P/N_P}$$

where:

- C_{RSV} and C_P are the numbers of RSV MAARI / RSV MAALRI cases meeting the considered definition in the RSV (low dose or high dose) and Placebo groups, respectively.
- N_{RSV} and N_P are the numbers of participants in the RSV (low dose or high dose) and Placebo groups, respectively.

The CI will be calculated using the exact method conditional on the total number of cases in both groups described by Breslow & Day (2).

Let $q = \frac{C_{RSV}}{C_{RSV}+C_P}$, the proportion of cases belonging to RSV group (low dose or high dose) among the total number of cases in the considered RSV vaccine group and Placebo group. Given the total number of cases, C_{RSV} has a binomial distribution ($C_{RSV}+C_P$, q). Thus, a CI for q may be constructed using the exact Clopper-Pearson method for binomial proportions (1).

As $\frac{q}{1-q} = \frac{C_{RSV}}{C_P}$, the VE estimate given above may be restated as follows:

$$VE = 1 - \frac{C_{RSV}/N_{RSV}}{C_P/N_P} = 1 - \frac{N_P}{N_{RSV}} \times \frac{q}{1-q}, \text{ which is a strictly decreasing function of } q.$$

Finally, for each efficacy endpoint, a CI of the VE will be constructed based on the CI of q .

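### Age at 12 months is a randomisation stratum, but no safety, shedding or infectivity analysis by age is pre-specified; only the main immunogenicity analyses use it

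*SAP*

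**What the plan says.** **Design.** Protocol 6.5: "At Visit 01, randomization will be stratified by cohort and by age sub-group", with the cut at 12 months. SAP 4.4.4.1 carries this into the data: "Following age groups will be derived, corresponding to stratification factor".

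**Where age is used.** SAP 5.1.2.2, at the end of its immunogenicity text: "Main immunogenicity analyses will be presented by baseline serostatus and age group". No other analysis is assigned to the age groups.

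**Where age is not used.**
- Primary safety (SAP 5.1.1.2): "At least the following parameters will be presented by vaccine group after each and any vaccination, in all participants regardless of baseline serostatus".
- Exploratory safety (SAP 5.1.3): "Analyses described in Section 5.1.1.2 will be presented by vaccine group after each and any vaccination by baseline serostatus".
- Shedding at D7 and D63, and infectivity at D56 and D84 (SAP 5.1.2.2): by arm and baseline serostatus.
- The general rule in SAP 5.1 names cohort, pooled cohorts, serostatus and overall. It does not name age.

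**The comparison rule.** SAP 5.1.1.2 allows an optional Bayesian comparison of Grade 3 or higher LRI and of Grade 3 fever, using counts for the whole arm. It recommends considering dropping a formulation if the posterior probability that the difference exceeds delta is high, for example 80%. The SAP gives delta no value. Protocol Section 15 uses 5% in a worked example with 20 per group.

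**The concern.** The plan looks at response by age but not at harm or attenuation by age. The protocol itself treats age as relevant to respiratory assessment. Its tachypnea definition (Section 9.1.1.3.5) changes threshold at about one year, so a pooled LRI rate mixes two definitions. Exclusion criterion 23 bars children born before 37 weeks only if they are under one year. Section 9.1.1.3 calls shedding and replication 7 days after vaccination the most quantifiable measure of attenuation, yet shedding has no age split.

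If the vaccine were less well attenuated in infants than in toddlers, the excess would be averaged over the whole arm. The trial is used to confirm a dose for later studies, so a reader of the planned tables could not tell an even, small excess from a larger one confined to infants. An age table added after unblinding would be post hoc.

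**Working it through.** **1. The plan's own figures.** Probability of at least one event is 1 − (1 − p)^n. Low dose: 1 − 0.97^100 = 0.952. High dose: 1 − 0.9625^80 = 0.953. Both reproduce the stated 95% (Protocol 12.5, SAP 5.5).

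**2. Dilution of a difference.** Let f be the share of each arm under 12 months, equal across arms, and d an excess present only in infants. The pooled excess is f × d. The documents give no value for f, so it is an assumption shown over a range. For an assumed d of 8 points: 0.3 × 8 = 2.4, 0.5 × 8 = 4.0, 0.7 × 8 = 5.6 points.

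**3. Dilution on the SAP's posterior.** Inputs: planned arms of 100 (low dose), 80 (high dose) and 120 (placebo) from SAP 5.5; posterior Beta(x + 1, n − x + 1) per arm from SAP 5.1.1.2; delta of 5 points from the Section 15 example. Assumed: all events in infants, none on placebo. Probabilities are by simulation, as the SAP specifies.

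| Set analysed | Low dose vs placebo | P(diff > 5 points) | High dose vs placebo | P(diff > 5 points) |
|---|---|---|---|---|
| Pooled | 5/100 vs 0/120 | 0.47 | 4/80 vs 0/120 | 0.50 |
| Infants, f = 0.3 | 5/30 vs 0/36 | 0.95 | 4/24 vs 0/36 | 0.94 |
| Infants, f = 0.5 | 5/50 vs 0/60 | 0.87 | 4/40 vs 0/60 | 0.86 |
| Infants, f = 0.6 | 5/60 vs 0/72 | 0.80 | 4/48 vs 0/72 | 0.79 |
| Infants, f = 0.7 | 5/70 vs 0/84 | 0.72 | 4/56 vs 0/84 | 0.72 |

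At f = 0.5, the pooled data need 8 low-dose or 6 high-dose events to reach 0.80; the infant stratum needs 5 or 4. At f = 0.7 the infant value is still well above the pooled one, but these event counts no longer cross 0.80.

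**4. Does the serostatus split do the same job?** SAP Table 5.2 expects 5% to 35% RSV-experienced. Take the low-dose arm of 100 with half under 12 months, and suppose every experienced child is a toddler, the most favourable case. The naive group then holds 50 infants plus 50 − 35 = 15 toddlers at the 35% rate (15/65 = 23% toddlers), or 50 − 5 = 45 toddlers at the 5% rate (45/95 = 47%). The split helps only in part, and least when few are experienced.

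**5. Precision lost by splitting.** The incidence observable with 95% probability is 1 − 0.05^(1/n). At f = 0.5: n = 50 gives 5.8% (low dose, from 3%); n = 40 gives 7.2% (high dose, from 3.75%).

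**The case against.** **Severe events in infants are not hidden.** Under Protocol 5.1.6, one acute-phase AESI of Grade 3 or above is an alert, as are more than one LRI above Grade 2 and Grade 3 fever in more than two participants. These are counts, so age pooling does not dilute them. At an assumed 10% rate, 40 infants yield at least one event with probability 1 − 0.9^40 = 98.5%. An alert can lead to case unblinding or an ad hoc IDMC review. This stands: a reader might infer that the trial could miss severe infant illness, and the documents do not support that. But the routine reviews are blinded and the alerts respond mainly to severe events. They give no planned between-arm comparison in infants and do not address lower-grade LRI or shedding.

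**Five points is not a margin of the plan.** A reader might infer that an infant excess could pass within a tolerated limit. Delta of 5% appears only in the Section 15 example, for Grade 3 LRI and fever. The SAP fixes no value, the method is optional, and the criterion is a posterior probability rather than a point difference. It serves here only as a yardstick, and not for LRI of any grade.

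**The protocol does not say this stratum is at greatest vaccine risk.** Section 1.4 says of some infants "since they are at highest risk for severe RSV-associated LRI", but those are aged 4 to 6 months, in a separate NIH study, and the risk is of RSV disease rather than under-attenuation. This trial enrols from 6 months. No text in the documents says that its infants under 12 months carry more vaccine risk than toddlers.

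**Stratifying does not oblige reporting by stratum.** True. The SAP's list is also a minimum that leaves room for an age table. Permitting one is not the same as planning it.

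**Conclusion.** The gap is confirmed on the text: the plan pre-specifies no safety, shedding or infectivity analysis by the randomised age strata. The consequence is a missing comparison, not a failure of safety monitoring or a flaw in the randomisation. If an excess were confined to infants, pooling would weaken it materially: 0.47 against 0.87 for five low-dose events and 0.50 against 0.86 for four high-dose events at a 50% share. The gap narrows as the infant share rises (0.72 in infants at 70%). These figures rest on an assumed age mix equal across arms, no toddler or placebo events, full planned enrolment with cohorts pooled, and the protocol's illustrative delta. They show what pooling would do; they are not evidence that such an excess exists.

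**What to change.** In SAP 5.1.1.2 and 5.1.2.2, add that AESIs (LRI first), fever, MAAEs, SAEs, D7 and D63 shedding, and infectivity will also be presented by arm within the two randomised age strata (<12 and ≥12 months), with 95% confidence intervals and labelled descriptive. Apply this at the unblinded interim, early and final analyses. At the early analysis, shedding and infectivity by age belong in the second step that SAP 5.4 already sets aside for them.

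Do not supply an age split by arm to the SMT's early safety data reviews. Those are summarised blinded, and the split would give the team comparative unblinded data.

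The cost is repeated tables on a variable that is already derived, with no new data. All analyses are descriptive, so no multiplicity adjustment is needed. The real price is the wider intervals shown above, which the table footnotes should state so that an empty cell in one stratum is not read as reassurance.
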